9.4 Protocol Violation/Deviation

The relevant protocol violations/deviations have to be defined by a systematic data review prior to database closure. For this purpose, protocol violations that occurred during the study such as violations of inclusion/exclusion criteria or forbidden concomitant medications or subject non-compliance will be assessed as 'major' or 'minor' by depending on their potential to interfere with the objectives of the study. Listings will be prepared to show the eligibility of all patients. Comprehensive justification for the classification of a protocol violation/deviation as "major" will be given in the integrated clinical study report.

The list of protocol violations/deviations will be reviewed by the Sponsor and finalized before locking the database.

Statistical Analysis Plan
Sponsor: [name], Inc

Study Number: NV-05-983-2020

Version: 2.0 Date: 06JAN2021

9.5 Data Handling

9.5.1 Imputation of Missing data

Efficacy: As the patients were in the hospital until discharge, missing data in the daily WHO clinical status scores were few. To facilitate the definition of the durable response as part of the primary efficacy endpoint which now requires five consecutive days of clinical status score at 4 or lower, a very limited and conservative imputation will be implemented to impute a missing clinical status score if adjacent to a valid score on both sides, the imputed score will be the higher (worse) of the two. For example, if Day 10 score is missing with Day 9 score of 5 and Day 11 score of 4, then the imputed Day 10 score will be 5.

Safety: To handle missing or partial AE and concomitant medication date, the following rules will be applied.

For partial start dates:

1. If the year is unknown, then do not impute the date but assign a missing value.
2. If the month is unknown, then:
 - a. If the year matches the year of the dose date, then impute the month and day of the dose date.
3. If the day is unknown, then:
 - a. If the month and year match the month and year of the first dose date, then impute the day of the dose date.
 - b. otherwise, assign "01"

For partial end dates:

1. If the year is unknown, then do not impute the date but assign a missing value.
2. If the month is unknown, then do not impute the date and mark as ongoing for AE and Concomitant medication.
3. If month is known but the day is unknown, then assign the last day of the month.

After implementing the rules above, to determine whether AEs (or medications) with missing start or stop dates are pretreatment or on/after treatment, the following strategy will be used:

1. If the start date and stop date are both missing, then the most conservative approach is taken and the AE (or medication) is considered to be treatment emergent (or concomitant medication).
2. If the start date is missing but the stop date is not missing and is on or after the day of study dose administration, then the most conservative approach is taken and the AE (or medication) is considered to be treatment emergent (or concomitant medication).

Statistical Analysis Plan
Sponsor: [name], Inc

Study Number: NV-05-983-2020

Version: 2.0 Date: 06JAN2021

3. If the start date is missing but the stop date is not missing and is before the day of first study dose and after the date of signed informed consent, then the AE (or medication) is considered to be before treatment (or prior medication).

4. If the start date is not missing but the stop date is missing, then the most conservative approach is taken and medication is considered to be concomitant while the AE is defined by start date.

If the Adverse Event Relationship flag is missing, the relationship for adverse event will be imputed and will be considered as possibly related. If the Adverse Event Severity flag is missing, the severity will be imputed with the maximum severity will be considered as severity.

9.6 Sample Size Calculation

Based on review of published literature, a hazard ratio of 1.25 is reported (adjusted for the stratification in randomization) for time to clinical improvement in COVID-19 patients receiving anti-viral intervention. The hazard ratio of 1.25 is also assumed to be constant throughout the study as per the assumptions of the Cox proportional hazards regression model with the expected average probability of the event over the course of the study to be 0.9 and 0.8 in test and control group respectively. Inequality testing of the hazard ratio using the Cox proportional hazards regression model with 371 subjects in Favipiravir group and 371 subjects in Placebo group achieves 80% power at the 0.05 significance level for an actual hazard ratio of 1.25 assuming the hazard ratio is 1 under the null hypothesis and that the total number of events achieved is 631. Based on the above assumption and considering the dropout rate to be 5%, overall, 390 patients will be randomized in each treatment group. i.e. 780 patients in total to be randomized in the study. The sample size is estimated using nQuery version 8.5.0.0 using Cox proportional hazard regression. Sample size will be re-estimated based on the analysis of results for the primary endpoint observed during interim analyses.

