randomization) for time to clinical improvement in COVID-19 patients receiving anti-viral interventions. The hazard ratio of 1.25 is also assumed to be constant throughout the study as per the assumptions of the Cox proportional hazards regression model with the expected average probability of the event over the course of the study to be 0.9 and 0.8 in test and control group respectively. Inequality testing of the hazard ratio using the Cox proportional hazards regression model with 371 subjects in Favipiravir group and 371 subjects in Placebo group achieves 80% power at the 0.05 significance level for an actual hazard ratio of 1.25 assuming the hazard ratio is 1 under the null hypothesis and that the total number of events achieved is 631. Based on the above assumption and considering the dropout rate to be 5%, overall, 390 patients will be randomized in each treatment group. i.e. 780 patients in total to be randomized in the study. The sample size is estimated using nQuery version 8.5.0.0 using Cox proportional hazard regression.

Sample size will be re-estimated based on the analysis of results for the primary endpoint observed during interim analyses. . Details of the interim analysis and futility assessment are provided in the Statistical Analysis Plan (SAP) for the Interim Analysis.

Study Endpoints:

Stage I:

Efficacy Endpoints:

Primary Efficacy Endpoint:

1. Time to resolution of hypoxia (Time frame: Up to 28 days)

This endpoint will be considered to have been met when the patient has attained a score of 4 or lower on the 10-point ordinal scale of clinical status and either of a) or b), and c) is met:

- a) Score is ≤ 4 on consecutive assessments over the next 5 days, if patient continues to remain in hospital (i.e., has not been discharged).

OR

Study code: NV-05-983-2020
 Protocol No.: CVD-04-CD-001
 Sponsor name: [name], Limited
 Clinical Study Protocol

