11.10 Sample Size Determination

Based on review of published literature,²⁶ a hazard ratio of 1.25 is reported (adjusted for the stratification in randomization) for time to clinical improvement in COVID-19 patients receiving anti-viral intervention. The hazard ratio of 1.25 is also assumed to be constant throughout the study as per the assumptions of the Cox proportional hazards regression model with the expected average probability of the event over the course of the study to be 0.9 and 0.8 in test and control group respectively. Inequality testing of the hazard ratio using the Cox proportional hazards regression model with 371 subjects in Favipiravir group and 371 subjects in Placebo group achieves 80% power at the 0.05 significance level for an actual hazard ratio of 1.25 assuming the hazard ratio is 1 under the null hypothesis and that the total number of events achieved is 631. Based on the above assumption and considering the dropout rate to be 5%, overall, 390 patients will be randomized in each treatment group. i.e. 780 patients in total to be randomized in the study. The sample size is estimated using nQuery version 8.5.0.0 using Cox proportional hazard regression.

Sample size will be re-estimated based on the analysis of results for the primary endpoint observed during interim analyses. Details of the interim analysis and futility assessment are provided in the Statistical Analysis Plan (SAP) for the Interim Analysis.

Study code: NV-05-983-2020
Protocol No.: CVD-04-CD-001
Sponsor name: [name], Limited
Clinical Study Protocol

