Appendix I: Interim Analysis Plan

A single unblinded interim analysis of the primary efficacy endpoint, that is, time to resolution of hypoxia, will be conducted. Resolution of hypoxia is defined as described in Section 10.6.1. This endpoint will be considered to have been met when the patient had attained a score of 4 or lower on the 10-point ordinal scale of clinical status used by the WHO in the SOLIDARITY trial, and either maintained the score of 4 or lower for five consecutive assessments over 5 days or was discharged after reaching the score of 4 or lower. In addition, the patient must also survive and not be readmitted to hospital due to COVID-19 related complications through Day 28 to be considered meeting the endpoint. To be performed when data for time to resolution of hypoxia become available for either the first 390 randomized subjects (50% of the target enrollment) or subjects enrolled by the end of year 2020, whichever is earlier, interim analysis will be conducted for three purposes: 1) Possible early stopping for demonstrated efficacy of the study treatment, 2) Possible early stopping for futility (lack of efficacy), and 3) Sample size reassessment. After reviewing the analysis, the DMC will make a recommendation concerning continuation of the study as planned, termination, or continuation with a larger sample size.

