The interim analysis for efficacy will be performed like the primary efficacy analysis detailed in Section [10.6.1](#) of the Statistical Analysis Plan for the final analysis. Time to resolution of hypoxia will be compared between the treatment groups using the Cox proportional hazard model with age, gender, and baseline score on the 10-point ordinal scale of clinical status as covariates. A Lan-DeMets alpha spending function approach will be adopted in order to maintain the overall Type-I error or alpha at the desired two-sided 0.05 level (Lan & DeMets, 1983). The boundary for possible early stopping for demonstrated efficacy will be determined using a Type I error rate of 0.005 (one-sided); that is, the null hypothesis of zero treatment effect will be rejected if the observed effect is in the direction of treatment benefit and it is significant with one-sided $p < 0.005$. If the trial is not stopped after the interim analysis, the final primary efficacy analysis conducted upon study completion will be based on an adjusted Type I error rate of two-sided 0.04521 (i.e., the result will be considered statistically significant for a Z-statistic ≥ 2.0027).

Assuming the Z-statistic does not reach the boundary for early stopping for demonstrated efficacy, an analysis will be conducted for possible early stopping for futility. A DMC recommendation of early stopping for futility will be based on two factors. The first factor is the conditional power, i.e., the probability of finding a significant beneficial treatment effect with adjusted Type I error rate of two-sided 0.04521 at the end of the study, given the current data and appropriate assumptions about the true treatment effect. The second factor is the estimated effect size from the interim analysis. The DMC may recommend the study be stopped for reasons of futility if either 1) the conditional power is very low (for example, 20% or lower), assuming a hazard ratio equal to the estimated hazard ratio from the current data, or 2) the upper limit of a 95% confidence interval for the difference in median time to resolution of hypoxia is < 1 day. The conditional

Statistical Analysis Plan
Sponsor: [name], Inc

Study Number: NV-05-983-2020

Version: 2.0 Date: 06JAN2021

power will be calculated as in Lachin (2005) and Chen, DeMets, & Lan (2004). Median times to resolution of hypoxia will be estimated by the Kaplan-Meier method.

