If the interim analysis results do not suggest early stopping for efficacy or futility, the DMC will consider whether to recommend an increase in sample size, following the method given by Chen, DeMets, & Lan (2004). Conditional power will be calculated under the assumption that the true underlying hazard ratio is the same as the estimate from the current data. If this conditional power is less than 80%, the increase in sample size necessary to make the conditional power 70%, 75%, or 80% will be calculated. If the conditional power with the currently planned sample size is $\geq 50\%$ and the sample size increment required for the desired power is less than approximately 1.5 times the original sample size, increasing sample size by this method will not affect the Type I error rate. In addition, simulations suggest the Type I error in this analysis will not be inflated for conditional power $\geq 20\%$ and $< 50\%$, as long as there is a stopping rule for very low conditional power (Lan & Trost, 1997). If the increase in sample size required to achieve a desired power is not feasible, a smaller increase may be made.

Two key secondary endpoints will also be analyzed in the interim analysis for considering by the DMC in their deliberations. These two endpoints are time to discharge from hospital and time to improvement from baseline of at least 2 points on the 10-point clinical status scale. Cox models and Kaplan-Meier analysis will be employed, as for the primary endpoint. Missing values will not be imputed.

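### The sample size text pairs a constant hazard ratio of 1.25 with event probabilities that imply 1.43, gives single-look power for a two-look design, and fixes a final boundary that is exact only at 50% information

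*SAP*

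**What the plan says.** The same calculation appears in SAP 9.6, Protocol 11.10 and the synopsis (Planned Sample Size). A hazard ratio of 1.25, taken from published literature, is assumed constant under the Cox model. For the event rates the plan takes "the expected average probability of the event over the course of the study to be 0.9 and 0.8 in test and control group respectively". In SAP 9.6, a design with 371 patients per arm, 742 in all, "achieves 80% power at the 0.05 significance level for an actual hazard ratio of 1.25". The synopsis claims the same power and gives its conditions as "assuming the hazard ratio is 1 under the null hypothesis and that the total number of events achieved is 631". After 5% dropout, 780 are to be randomized. The text adds that sample size will be re-estimated at the interim, and SAP 9.7 refers the reader to Appendix I.

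Appendix I plans one unblinded interim with data from "either the first 390 randomized subjects (50% of the target enrollment) or subjects enrolled by the end of year 2020, whichever is earlier". Its main features are:

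- **Efficacy.** The trial may stop at one-sided p < 0.005. A Lan-DeMets approach is adopted "in order to maintain the overall Type-I error or alpha at the desired two-sided 0.05 level". If the trial continues, the final analysis "will be based on an adjusted Type I error rate of two-sided 0.04521", that is, Z of at least 2.0027.
- **Futility.** "The DMC may recommend the study be stopped for reasons of futility if either 1) the conditional power is very low", with 20% or lower given as an example, or if a second criterion based on the difference in medians is met.
- **Size increase.** If conditional power is below 80%, "the increase in sample size necessary to make the conditional power 70%, 75%, or 80% will be calculated".

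**The concern.** The sample size text contains two mismatches, and Appendix I a third.

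First, under proportional hazards with the same 28-day time frame in both arms, the hazard ratio and one event probability determine the other probability. The plan states all three, and they do not agree. The expected number of events from 742 patients therefore depends on which probability is kept.

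Second, a reader will take 80% as the power of the planned trial. The sample size sections show no adjustment for the interim look or for the stricter final test.

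Third, the final critical value is a fixed number, while the interim has a calendar trigger that can bring it forward. If the interim comes early, the fixed value no longer delivers the overall level that Appendix I says it maintains.

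At stake are the consistency of the stated assumptions, an accurate power statement, and exact control of the Type I error in a confirmatory trial.

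**Working it through.** **Inputs.** Hazard ratio 1.25, probabilities 0.9/0.8, 371 per arm, 631 events, 80% power (SAP 9.6, Protocol 11.10, synopsis). Two-sided 0.05 overall, interim bound one-sided 0.005 (Z = 2.5758), final Z = 2.0027, interim at 390 of 780 or earlier (Appendix I).

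**1. The plan's own figure.** Schoenfeld's formula with 1:1 allocation gives

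events = 4 × (1.95996 + 0.84162)² / ln(1.25)² = 630.5, so 631.

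Power at 631 events: the drift is ln(1.25) × √631 / 2 = 2.8027, and Φ(2.8027 − 1.9600) = 80.03%. Expected events are 371 × (0.9 + 0.8) = 630.7. The stated figures reproduce as a single test at two-sided 0.05. At one-sided 0.05 only 497 events would be needed. The two probabilities enter only through their mean, 0.85.

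**2. Consistency of the inputs.** With a constant hazard ratio, HR = ln(1 − p_test) / ln(1 − p_control). For 0.9 and 0.8 this is ln(0.1)/ln(0.2) = 1.431. Holding 1.25:

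- control 0.80: p_test = 1 − 0.2^1.25 = 0.866, and 371 × (0.80 + 0.8663) = 618 events;
- test 0.90: p_control = 1 − 0.1^(1/1.25) = 0.842, and 371 × (0.90 + 0.8415) = 646 events.

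**3. Power with both looks.** The two test statistics are bivariate normal with correlation √t. At information fraction t = 0.5 and with no futility stopping,

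power = P(Z1 > 2.5758) + P(Z1 ≤ 2.5758 and Z2 > 2.0027).

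For 631 events, Z1 has mean 2.8027 × √0.5 = 1.982, and the two terms are 27.6% and 51.6%, together 79.2%.

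| Events | Fixed, two-sided 0.05 | Two looks, Appendix I boundaries |
|---|---|---|
| 618 | 79.2% | 78.4% |
| 631 | 80.0% | 79.2% |
| 646 | 80.9% | 80.2% |

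**4. The final boundary.** Under the null, with 0.005 used at the interim and no futility stopping:

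| Information at interim | One-sided alpha if Z = 2.0027 is kept | Final Z that gives 0.025 |
|---|---|---|
| 50% | 0.0250 | 2.003 |
| 40% (assumed) | 0.0255 | 2.013 |
| 30% (assumed) | 0.0260 | 2.023 |

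At 60% information the fixed value gives 0.0244, so only an earlier interim exceeds the level. At 631 events the adjusted final Z gives power of about 79.0% at 40% and 78.6% at 30%.

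**The case against.** The strongest reply is that no stated result is wrong. The 631 events, 371 per arm and 80% all reproduce, the events follow from 1.25 alone, and each effect is about one point of power or less. SAP 9.6 mentions re-estimation and 9.7 points to Appendix I, so the interim is not hidden. The DMC charter, to which the protocol ties the interim plan, is not available and may report more. The 40% and 30% fractions are assumptions, since the documents do not give enrolment at the end of 2020. All of this stands, and it limits the point to correcting the text and the boundary rule. It does not remove the conflict between 1.25 and 0.9/0.8, which appears in all three places, or the mismatch between a fixed boundary and a flexible interim date.

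A reader might go further in four ways that the documents do not support.

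- **That 1.43 was the intended effect, so about 245 events would do.** The plan cites 1.25 from the literature, repeats it as the actual ratio, and derives 631 from it. Nothing points to 1.43.
- **That true power is about 73%.** That figure (73.3% at 631 events) needs the 20% example to be followed every time at 50% information and no size increase. About 16% of trials with a true ratio of 1.25 would then stop for futility, but power falls by only about 6 points (79.2 − 73.3 = 5.9), because many of those trials would have failed at the end anyway. The guideline is advisory, and a size increase could recover much of the loss.
- **That the Type I error is seriously inflated.** The excess is at most 0.001 one-sided at the fractions examined. If the futility example were always followed, alpha would fall below 0.025. An advisory rule cannot be relied on for that, which is why the boundary should hold without it.
- **That the missing table of futility and size-increase properties is an error.** It is detail that could be added, and the charter may hold it.

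**Conclusion.** The point holds, and it is small. The constant ratio of 1.25 and the probabilities 0.9/0.8 cannot both be right under proportional hazards with common 28-day follow-up. Consistent inputs move the expected events from 742 patients to 618 or 646, and fixed-design power to 79.2% or 80.9%. The stated 80% is a single-look figure. The Appendix I efficacy boundaries make it 79.2% at 631 events, or 78.4% and 80.2% at 618 and 646, assuming 50% information and no futility stopping. The final value of 2.0027 is correct at 50% information and slightly too lenient before that: 0.0255 or 0.0260 one-sided at the assumed 40% or 30%, against the intended 0.025. The 631 events, the 780 patients and the futility guideline need not change.

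**What to change.** (a) In SAP 9.6, Protocol 11.10 and the synopsis, keep 1.25 and replace 0.9/0.8 with one consistent pair, giving the matching expected events from 742 patients and the fixed-design power: 0.866/0.80 with 618 events and 79.2%, or 0.90/0.842 with 646 events and 80.9%.

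(b) Beside it, state the matching two-look power without futility stopping: 78.4% or 80.2%.

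(c) In Appendix I, replace the fixed 0.04521 with a final boundary computed from the actual information fraction at the interim, given the 0.005 already spent: Z of 2.003 at 50%, 2.013 at 40%, 2.023 at 30%.

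The cost is a few corrected sentences in three places and one sentence in Appendix I. The downside is a slightly stricter final test if the interim is early. Enrolment and the futility guideline stay as they are.

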9.7 Interim Analysis

Details of the interim analysis are provided in the appendix I "Interim Analysis".

9.8 Statistical Software

All statistical analyses will be performed with SAS[®], Version 9.4 or later.

10 Statistical Analyses

10.1 Subject Disposition

Subject disposition will be tabulated with number and percentages of patient's screen failed, randomized, received one or more doses of study treatment, completed the study according to the protocol or discontinued the study prematurely. The patients who prematurely discontinued the study and the reasons for their discontinuation will be presented. The disposition table will be summarized using "Screened population" by treatment group.

Statistical Analysis Plan
Sponsor: [name], Inc

Study Number: NV-05-983-2020

Version: 2.0 Date: 06JAN2021

10.2 Demographic Data and Baseline Characteristics

The demographic data and baseline characteristics will be summarized using descriptive statistics or by frequency and percentage for the applicable parameters using SAF Population by treatment group.

- Gender
- Age
- Race
- Height
- Weight
- Nationality
- BMI
- No. of days since first onset of symptoms associated with COVID-19 (at baseline)
- Clinical Status by 10-point ordinal scale
- Clinical Status by 8-point ordinal scale
- National Early Warning Score (NEWS Score)
- COVID-19 associated symptoms
- RT-PCR (Was RT-PCR test performed for SARS-CoV 2 ?)
- RT-PCR result
- Chest X-ray total RALE score

